2.1.3 General definitions

2.1.3.1 Study drug

In this document, ‘study treatment’ or ‘study drug’ will be used to refer to investigational therapy assigned to a patient. Specifically, for this double-blind trial, study treatment refers to QAW039 150 mg, QAW039 450 mg or placebo as assigned to a patient at randomization.

2.1.3.2 Date of first administration of study drug

The ‘date of first administration of the study drug’ is derived as the first date when a non zero dose of study drug is administered as per the Dosage Administration (e)CRF. The date of first administration of study treatment will also be referred as *start of study treatment*.

2.1.3.3 Date of last administration of Study Drug

The ‘date of last administration of the study drug’ is derived as the last date when a non zero dose of study drug is administered as per the Dosage Administration (e)CRF.

2.1.3.4 Study Day

The study day, describes the day of the event or assessment date, relative to the reference start date.. The date of first administration of the study drug is defined as Day 1 and the day before the first administration of the study drug is defined as Day -1.

Therefore, for a particular date, study day will be calculated as follows :

- The date of the event (visit date, onset date of an event, assessment date etc.) – reference start date + 1 if event is on or after the reference start date;
- The date of the event (visit date, onset date of an event, assessment date etc.) – reference start date if event precedes the reference start date.

The reference start date for safety assessments (e.g. adverse events, laboratory abnormality occurrence, vital sign measurements, dose interruption etc.) is the start of study treatment. The reference start date for all other, non-safety assessments (i.e., eDiary, patient reported outcomes (PRO)) is the date of randomization.

The study day will be displayed in the data listings. If an event starts before the reference start date, the study day displayed on the listing will be negative.

2.1.3.5 Time unit

A month length is 30.4375 days (365.25/12). If duration is reported in months, duration in days will be divided by 30.4375.

2.1.3.6 Baseline

For efficacy evaluations, the last non-missing assessment, including unscheduled assessments on or before the date of randomization is taken as “baseline” value or “baseline” assessment. In the context of baseline definition, the efficacy evaluations also include PRO and performance status.

For safety evaluations, the last available assessment on or before the date of start of study treatment is taken as “baseline” assessment.

If patients have no value as defined above, the baseline result will be missing.

- Vital signs include body temperature, pulse rate and systolic and diastolic blood pressures. Baseline vital signs are defined as the last available assessment taken pre-dose on Day 1. If this assessment is missing or not confirmed to be pre-dose, the last value prior to the first dose will be used for baseline. Otherwise, the vital sign baseline will be set to missing without imputation.
Baseline height and weight are defined as the last measurements taken prior to first dose of study treatment. Missing baseline values will not be imputed.
- Baseline electrocardiogram (ECG) is defined as the last scheduled assessment taken prior to the first dose of study drug on screening. If the value on screening is missing (or not confirmed to be pre-dose), then the last value prior to the first dose will be used for baseline. Otherwise, the ECG baseline will be set to missing without imputation. Missing ECG baseline values will not be imputed.
- Laboratory data include hematology and biochemistry. Baseline hematology and biochemistry are defined as the last available assessment taken prior to first dose of study treatment on Day 1. If the pre-dose measurement on Day 1 is missing (or was not confirmed to be pre-dose), then the last value prior to the first dose will be used. Otherwise, the baseline laboratory data will be set to missing. Missing laboratory baseline values will not be imputed.

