### 5.2 Exclusion criteria

Subjects meeting any of the following criteria are not eligible for inclusion in this study.

1. Asthma exacerbation, within 6 weeks prior to screening that required systemic corticosteroids, hospitalization, or emergency room visit. When patients experience an exacerbation between screening and the end of the 4-week Run-in period, and prior to randomization, they will be considered screen failures and can be eligible for re-screening only once the required 6 weeks post exacerbation window has passed.
2. Chronic/maintenance use of oral corticosteroids (OCS) or systemic corticosteroids (SCS) defined as any continuous use of OCS/SCS for a period of 1 month or more within 1 year of Screening.
3. Patients who, in the judgement of the Investigator, have a clinically significant ECG abnormality such as, but not limited to, sustained ventricular tachycardia or clinically significant second or third degree AV block without a pacemaker.
4. Patients with a history of familial long QT syndrome or known family history of Torsades de Pointes.
5. Patients with a resting QTcF (Fridericia)  $\geq 450$  msec (males) or  $\geq 460$  msec (females) at screening.
6. Use of biologics (omalizumab, mepolizumab, reslizumab, dupilumab, benralizumab etc., for asthma or any other indications) that has potential to interfere/affect asthma or NP disease progression, within 6 months of the start of the Run-in period.
7. Use of medication for sino-nasal symptoms (antibiotics with or without OCS) within 30 days of Screening or during the Run-in period.

8. Use of tetracycline (e.g. doxycycline) or macrolide antibiotics specifically within the 8 weeks prior to the start of the Run-in period due to the influence they have on Nasal Polyps.
9. Any contra-indications to inhaled or nasal steroids e.g. narrow angle glaucoma, or any other as decided by the Investigator.
10. Pregnant or nursing (lactating) women
11. Women of child-bearing potential, defined as all women physiologically capable of becoming pregnant, unless they are using basic methods of contraception during dosing of investigational drug. Basic contraception methods include:
  - Total abstinence (when this is in line with the preferred and usual lifestyle of the subject. Periodic abstinence (e.g., calendar, ovulation, symptothermal, post-ovulation methods) and withdrawal are not acceptable methods of contraception

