**Table 8-1 Assessment Schedule**

Period	Screening			Treatment					
Visit Name	Screening	Run-in 		Treatment				EOT or TD	Follow-up
Days	-42 to -28	-28 to -1	1	1	28	56	84	112	124
Weeks	-6 to -4	-4 to -1	1	1	4	8	12	16	18
Informed consent	X								
Inclusion / Exclusion criteria	X	X	X						
Demography	X								
Physical Examination	S							S	
Medical history/current medical conditions	X								
Surgeries and Procedures	X								
Prior medications	X								
Safety Follow up Call									S
ACQ-5	X								
Vital Signs	X	X	X		X	X	X	X	
Body Height	X								
Electrocardiogram (ECG)	X		X					X	
Body Weight	X								
Pregnancy Test (serum)	X								
Pregnancy Test (Urine)			S		S	S	S	S	
Hematology	X		X			X		X	
HbA1C	X							X	
Clinical Chemistry	X		X			X		X	
Urinalysis	X		X						
Check IMP Compliance					S	S	S	S	
Contact IRT (IVRS/IWRS)	S	S	S	S	S	S	S	S	
Randomization				S					

Period	Screening			Treatment					
Visit Name	Screening	Run-in 		Treatment				EOT or TD	Follow-up
Days	-42 to -28	-28 to -1	1	1	28	56	84	112	124
Weeks	-6 to -4	-4 to -1	1	1	4	8	12	16	18
Study Drug Dispensation				S	S	S	S		
Study drug administration				Daily					
SoC/Rescue Medication Dispense		S	S	S	S	S	S		
Adverse Events	X	X	X		X	X	X	X	X
Serious Adverse Events	X	X	X		X	X	X	X	X
Concomitant medications	X	X	X		X	X	X	X	X
Liver Event Monitoring 	X	X	X	X	X	X	X	X	X
Renal Event Monitoring 	X	X	X	X	X	X	X	X	X
Nasal Endoscopy 	X		X			X		X	
Nasal Congestion Score Questionnaire	X	X	X		X	X	X	X	
QoL Questionnaire (SNOT-22)	X	X	X		X	X	X	X	
Smell Assessment (UPSIT)	X	X	X		X	X	X	X	
Study completion information								X	

X Assessment to be recorded in the clinical database or received electronically from a vendor

S Assessment to be recorded in the source documentation only

 Assessments at Run-in Day 1 will be performed prior to Randomization. Run-in Day 1 and the Treatment Day 1 visit will take place on the same day if the patient is randomized

 Please refer to protocol [Section 10.2.1](#)

 Please refer to protocol [Section 10.2.2](#)

 Nasal polyp score will be determined by central reading.

 [REDACTED]

 For patient familiarization with device only.

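### The SAP takes the ECG baseline from screening although a pre-dose Day 1 ECG is scheduled, so some QTcF abnormalities present before dosing can be tabulated as new on treatment

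*SAP*

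**What the plan says.** SAP 2.1.3.6 opens its safety part with a general rule: "the last available assessment on or before the date of start of study treatment is taken as" baseline. Rules for each type of measurement follow.

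- Vital signs: "Baseline vital signs are defined as the last available assessment taken pre-dose on Day 1".
- Hematology and biochemistry: "the last available assessment taken prior to first dose of study treatment on Day 1".
- ECG: "the last scheduled assessment taken prior to the first dose of study drug on screening". The fallback reads: "If the value on screening is missing (or not confirmed to be pre-dose), then the last value prior to the first dose will be used".

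Protocol Table 8-1 places ECGs at three visits: Screening (Days -42 to -28), Run-in Day 1 and end of treatment (Day 112). Its first footnote says "Assessments at Run-in Day 1 will be performed prior to Randomization", and that Run-in Day 1 and Treatment Day 1 fall on the same day for a randomized patient.

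Protocol 5.2, criterion 5, excludes a screening QTcF of 450 msec or more in men and 460 msec or more in women. SAP 2.8.1 (Table 2.8.1) counts newly occurring or worsening QTcF at the same two limits and above 500 msec, and groups change from baseline as below 30, 30 to 60 and above 60 msec.

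**The concern.** When both pre-dose ECGs exist, the ECG rule as worded passes over the one taken on the day of first dosing in favour of one taken 4 to 6 weeks earlier. The SAP gives no reason for treating ECG differently from vital signs and laboratory data.

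The screening QTcF is also the value on which patients were admitted. It is cut off at the very limits that later define an abnormality, so a correctly enrolled patient cannot be abnormal at baseline in Table 2.8.1. A pre-existing elevation that appears on Day 1 is invisible to the table.

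The ECG tables have some weight here. Protocol 4.5 says that no formal QTc study has been completed and reports an imbalance in cardiac adverse events in an earlier study. Protocol 8.4.2 uses single tracings from site machines, and only one post-dose ECG is scheduled.

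**Working it through.** **No figure to reproduce.** The plan attaches no number to this rule, so the check compares the rules, then counts, then illustrates size.

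**Step 1: which ECG each rule picks.** Take a randomized patient with ECGs at Screening and at Run-in Day 1. The general safety rule picks Run-in Day 1. The vital-sign and laboratory rules, applied by analogy, also pick Day 1. The ECG rule picks Screening, because its fallback is not triggered. The gap is 28/7 = 4 to 42/7 = 6 weeks.

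**Step 2: counting.** SAP 2.7.7.2 requires a non-notable baseline for a newly occurring value. It is written for laboratory data and extended to vital signs in 2.8.2; assume it holds for ECG too. Let A be the patients at or above their sex-specific limit on treatment, and B those at or above it on Day 1 before dosing.

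- Screening baseline: by criterion 5 no correctly enrolled patient is notable at baseline, so the count is |A|.
- Day 1 baseline: the count is |A and not B|.
- Difference: |A and B|, which is never negative.

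The direction therefore follows from the documents alone. It applies to the sex-specific rows of Table 2.8.1. It does not carry over fully to the separate list in SAP 2.8.1 that uses 450 msec for both sexes, because a woman may enter with a screening QTcF of 450 to 459 msec.

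**Step 3: size, under assumptions.** The documents give no QTcF mean or SD. The values assumed are mean 405, 415 or 425 msec, between-patient SD 15 or 20, and within-patient SD 8 or 12. Each of the three QTcF values is the patient's own mean plus independent error, with no drug effect and 2,000,000 draws per scenario. A patient enters only if the screening value is below 450 (the male limit, applied to everyone). The two quantities compared are:

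- screening baseline: P(end of treatment ≥ 450, given screening < 450)
- Day 1 baseline: P(end of treatment ≥ 450 and Day 1 < 450, given screening < 450)

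| Mean / between SD / within SD | New, screening baseline | New, Day 1 baseline | Ratio | Per 93 patients | Excess |
|---|---|---|---|---|---|
| 405 / 15 / 8 | 0.29% | 0.23% | 1.26 | 0.27 vs 0.21 | 0.06 |
| 415 / 15 / 12 | 2.54% | 2.01% | 1.26 | 2.36 vs 1.87 | 0.49 |
| 415 / 20 / 12 | 3.88% | 2.71% | 1.43 | 3.61 vs 2.52 | 1.09 |
| 425 / 20 / 12 | 7.58% | 4.89% | 1.55 | 7.05 vs 4.54 | 2.51 |

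Over all 12 scenarios the ratio runs from 1.17 to 1.64 and the excess from 0.06 to 2.51 patients of 93, or at most 2.51/3 = 0.84 per arm of 31.

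**Step 4: change categories.** Measured from screening, a rise of 30 msec or more occurs in 0.40% to 4.39% of patients; measured from Day 1, in 0.40% to 3.88%. The largest gap within one scenario is 4.39 - 3.86 = 0.53 percentage points, or 0.0053 × 93 = 0.5 patients.

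**The case against.** **The wording may not mean the screening visit.** As Table 8-1 reads in the available text, the Screening period heading seems to cover the run-in columns. The period would then hold two scheduled ECGs, and the last of them is Run-in Day 1. Asking whether an ECG is confirmed pre-dose also makes little sense 4 to 6 weeks before dosing. This stands as a real ambiguity. Against it, the fallback sets the screening value apart from the last value before the first dose, which fits the screening visit better. On either reading the sentence needs repair, because two programmers could choose different ECGs.

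**A specific rule may displace a general one.** True, so this is better called an unexplained exception than a flat contradiction.

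**The definition is borrowed.** SAP 2.8.1 uses newly occurring and worsening without defining them for ECG. The counting argument depends on the laboratory definition. If worsening were instead read as an abnormal baseline that becomes more abnormal, some patients already high on Day 1 would re-enter the combined count, and the excess would shrink.

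**The effect is small and the data stay visible.** Both pre-dose ECGs precede randomization, so with no drug effect the excess is expected to be the same in each arm. All databased safety data are listed, so recorded Day 1 ECGs can still be inspected. Both points stand. They limit the consequence but do not justify the rule.

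**The simulation is only illustrative.** It applies the male limit to everyone and rests wholly on assumed QTcF values.

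**Conclusion.** The point holds as an unexplained, possibly accidental, baseline rule that affects a planned safety table. If it is followed as worded, and if the laboratory definition applies to ECG, a patient at or above the limit both on Day 1 before dosing and on treatment is reported as a new on-treatment QTcF abnormality. The change categories are likewise measured from a value truncated by eligibility. The documents establish the direction only. The size, about 0 to 3 of 93 patients over the three arms, depends on the assumed means and SDs.

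Four stronger readings are tempting, and the documents support none of them.

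- A reader might infer that every patient who is high on Day 1 is counted as new. SAP 2.1.3.7 limits post-baseline values to those after the start of treatment, so the patient must also be high on treatment.
- A reader might infer that fevipiprant would look worse than placebo. The inflation should be shared by all arms; it raises absolute incidence and adds noise.
- A reader might infer a distorted mean QTcF change. SAP 2.8.1 and the ECG paragraph of Protocol 12.5.1 plan categorical summaries only.
- A reader might infer that medication changes during run-in make the screening ECG unsuitable. No section links those changes to QTcF.

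**What to change.** In SAP 2.1.3.6, define the ECG baseline as the last available ECG before the first dose. This is normally Run-in Day 1, with the screening ECG used only if the Day 1 ECG is missing or not confirmed pre-dose. In SAP 2.8.1, state that the definition of newly occurring and worsening in 2.7.7.2 applies to ECG. Check the worsening sentence in 2.7.7.2 at the same time: as written it too requires a non-notable baseline, which leaves it hard to tell apart from newly occurring.

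The cost is two or three sentences and the matching derivation in the analysis program. The Day 1 ECG is already scheduled for the database, so no visit, assessment or protocol change is needed. If the screening ECG is intended, the SAP should give the reason.

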2.1.3.7 Post-baseline measurement

- Post baseline measurements are defined as those assessments after the start of study treatment.

2.1.3.8 Change from baseline

- When change from baseline is of interest, the following formula will be used for each scheduled visit and time-point where baseline and post-baseline values are both available:
- Change from baseline = post-baseline value – baseline value; and

- If baseline or post-baseline values are missing, then the change from baseline will be missing.

2.1.3.9 On-treatment assessment/event and observation periods

The overall observation period will be divided into three mutually exclusive segments:

1. **pre-treatment period**: from day of patient's informed consent to the day before first administration of study treatment
2. **on-treatment period**: from date of first administration of study treatment to date of last actual administration of any study treatment +1 day (including start and stop date)
3. **post-treatment period**: starting at day 1 after last administration of study treatment.

Safety summaries (tables, figures) include data from the pre-treatment period (to display the baseline status e.g. for ECG) and the on-treatment period. Data from the post-treatment period with the exception of deaths should not be included unless requested from Health Authorities or external committees.

In particular, summary tables for adverse events (AEs) will summarize only on-treatment events, with a start date during the on-treatment period, the so-called **treatment-emergent** AEs.

However, all safety data (including those from the post-treatment period) will be listed and those collected during the pre-treatment and post-treatment period are to be flagged.

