
Data analysis
	
Approximately 93 patients will be randomized in 1:1:1 ratio in either of the 3 arms fevipiprant 450 mg dose, fevipiprant 150 mg dose or placebo in addition to standard of care.
 
Primary Objective:
 
The primary aim of the study is to evaluate a change in nasal polyp size with fevipiprant (150mg or 450mg once daily, separately) as compared to placebo. This will be evaluated by using the NPS) which is assessed by nasal endoscopy. The total NPS is recorded as the sum of the right and left nostril scores with a range of 0 to 8. A decrease in the NPS is considered a favorable outcome.
 
The analysis of the primary endpoint will be conducted according to the intention to treat principle using the full analysis set (FAS) population and using a mixed model repeated measures (MMRM) approach.
 
Secondary Objectives:
 
 
• Nasal Congestion Score: The change in NCS will be analyzed using an MMRM model.
 
• Quality of Life (SNOT-22): The treatment group difference in terms of change from baseline at Week 16 in SNOT-22 will be estimated using an MMRM model.
 
• Smell (UPSIT): The treatment group difference in terms of change from baseline at Week 16 in UPSIT will be estimated using an MMRM model.
 
• Safety and Tolerability: For all safety analyses, the safety set will be used. All listings and tables will be presented by treatment group. Safety summaries will be primarily based on on-treatment data with selected tables also presented for the all data after the first intake of study drug, while all databased safety data will be listed. The on-treatment period lasts from the date of first administration of study treatment to 30 days after the date of the last actual administration of any study treatment.
 

Key words
	
Efficacy and safety of QAW039, nasal polyp score, nasal congestion score, quality of life, smell, nasal polyposis, concomitant asthma, female and male patients ≥ 18 years

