#### **Adverse events**

Adverse events starting on or after the time of first intake of study drug and until the 30 days after the last intake of study drug will be classified as treatment-emergent adverse events. Any adverse events that started during the study after informed consent before the time of first intake

of the study drug will be classified as a prior adverse event and not included in tabulations of treatment emergent adverse events.

The following treatment emergent adverse event summaries will be produced,

- overall by system organ class and preferred term,
- overall by system organ class and preferred,
- overall by system organ class, preferred term and maximum severity,
- suspected drug related adverse events by system organ class and preferred term, and
- adverse events leading to permanent discontinuation of study drug by system organ class and preferred term.

Serious adverse events, non-serious adverse events, adverse events requiring dose adjustment or study-drug interruption adverse events requiring additional therapy during the on-treatment period will be summarized.

The adverse events of special interest (AESI) will be listed and summarized by treatment group.

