The statistical analysis plan (SAP) describes all planned analyses for the Clinical Study Report (CSR) of study QAW039A2322, a phase IIIB, 16 week multicenter, randomized, double-blind, parallel-group, placebo-controlled study of fevipiprant once daily plus standard-of-care (SoC) for assessment of the efficacy in reduction of nasal polyp size in patients with nasal polyposis and concomitant asthma

The content of this SAP is based on the protocol of QAW039A2322 version v03.

The purpose of the statistical analysis plan is to describe the implementation of the statistical analysis planned in section 12 of the study protocol. Data will be analyzed by Novartis according to the data analysis section 12 of the protocol which is available in [Appendix 16.1.1 of the CSR](#). Important information is given in the following sections and the details will be provided, as applicable, in [Appendix 16.1.9 of the CSR](#).

[figure not shown]

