2.7.3 Handling of missing values/censoring/discontinuations

Despite all attempts to ensure complete follow-up for all patients, some patients may not be followed for nasal polyp size for the whole planned study duration of 16 weeks. The primary analysis will be done using a Mixed Model Repeated Measures (MMRM) approach. Under the assumption that the missing values are missing at random (MAR), this provides asymptotically unbiased and consistent estimates of the treatment effects.Safety analyses

2.7.4 To evaluate the general safety and tolerability of fevipiprant (150 mg and 450 mg, separately) as compared to placebo.

Safety and tolerability assessments would be based on the incidence of adverse events and serious adverse events, as well as vital signs, clinical laboratory evaluation, and 12-lead electrocardiogram findings.

For all safety analyses, the safety set will be used. All listings and tables will be presented by treatment group. Safety summaries will be primarily based on on-treatment data with selected tables also presented for all data after the first intake of study drug, while all databased safety data will be listed. The on-treatment period lasts from the date of first administration of study treatment to 1 day after the date of the last actual administration of any study treatment.

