2.7.5 Adverse events (AEs)

Adverse events after informed consent including asthma exacerbations will be listed.

Adverse events starting on or after the day of the first intake of study drug and until the day after the last intake of study drug will be classified as treatment emergent adverse events. Adverse events that started during the study after informed consent and before the day of the first intake of study drug will be classified as prior adverse events and not included in tabulations of treatment emergent adverse events.

The number and percentage of patients who reported TEAEs will be summarized by primary system organ class (SOC), preferred term (PT), and treatment group for

- all adverse events (AEs)
- all AEs by maximum severity
- AEs suspected to be related to study drug
- AEs by standardized MedDRA query (SMQ) level serious AEs (SAEs)
- AEs leading to permanent study drug discontinuation
- Serious adverse events

Unless otherwise specified, primary system organ classes will be sorted alphabetically and, within each primary system organ class, the preferred terms will be sorted in descending order of frequency in the QAW039 150 mg once daily and QAW039 450 mg once daily treatment group. If a patient reported more than one AE with the same preferred term, the AE will be counted only once. If a patient reported more than one AE within the same primary system organ class, the patient will be counted only once at the system organ class level. In addition, the most frequent AEs will be presented by preferred term in descending order of frequency in the QAW039 150 mg QAW039 450 mg once daily treatment group.

Serious adverse events will also be summarized.

In addition, the most frequent AEs will be presented by preferred term in descending order of frequency in the QAW039 150 mg once daily treatment group.

All adverse events and related preferred terms and system organ class will be categorised using latest MedDRA version available at the time of data analysis.

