2.7.5.2 Adverse events reporting for safety disclosure

For the legal requirements of clinicaltrials.gov, two required tables on TEAEs which are not SAEs with an incidence greater than a certain threshold based on the final database and on treatment emergent serious adverse events and SAEs suspected to be related to study drug will be provided by system organ class and PT on the safety set population.

If for a same patient, several consecutive AEs (irrespective of study drug causality, seriousness and severity) occurred with the same SOC and PT:

- a single occurrence will be counted if there is ≤ 1 day gap between the end date of the preceding AE and the start date of the consecutive AE
- more than one occurrence will be counted if there is > 1 day gap between the end date of the preceding AE and the start date of the consecutive AE

For occurrence, the presence of at least one SAE / SAE suspected to be related to study drug / non SAE has to be checked in a block e.g., among AE's in a ≤ 1 day gap block, if at least one SAE is occurring, then one occurrence is calculated for that SAE.

The number of deaths resulting from SAEs suspected to be related to study drug and SAEs irrespective of study drug relationship will be provided by SOC and PT.

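### The SAP cuts the on-treatment and treatment-emergent window from 30 days after last dose to 1 day and does not declare the change

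*SAP*

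**What the plan says.** **Protocol.** The summary and section 12.5.1 both define the on-treatment period as running from first administration "to 30 days after the date of the last actual administration of any study treatment". The adverse-event text of 12.5.1 says that events starting from first intake "until the 30 days after the last intake of study drug will be classified as treatment-emergent adverse events".

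**SAP.** The introduction gives the SAP's purpose as to "describe the implementation of the statistical analysis planned in section 12 of the study protocol". Its definitions differ from that section:

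- 2.1.3.9 ends the on-treatment period early: from first administration "to date of last actual administration of any study treatment +1 day". Section 2.7.4 repeats the 1-day limit.
- 2.7.5 says that AEs from first intake "until the day after the last intake of study drug will be classified as treatment emergent adverse events".
- 2.7.6 limits the main death summary to last dose + 1 day, and adds a table of all deaths after first dose.
- 2.7.7, 2.8.1 and 2.8.2 treat laboratory, ECG and vital-sign values taken more than 1 day after last intake as post-treatment and do not summarise them.
- 2.1.3.9 adds: "Data from the post-treatment period with the exception of deaths should not be included unless requested from Health Authorities or external committees". All safety data are still listed, with pre- and post-treatment records flagged.
- 2.7.4 promises "selected tables also presented for all data after the first intake of study drug" but does not say which tables.
- Section 4, on changes to protocol-specified analyses, records that none applies.

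**The concern.** General safety against placebo is a stated secondary objective. The protocol has a 2-week follow-up to gather safety data, and SAE reporting runs for 30 days after last dose (Protocol 10.1.3), which matches its own window. The SAP removes almost all of that time from the tables that show incidence by arm, and gives no reason.

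Two kinds of data are affected.

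1. AEs with onset in follow-up. They drop out of the TEAE tables, the special-interest tables and the registry disclosure tables ("two required tables on TEAEs which are not SAEs" above a threshold, and the serious-event counterpart), all of which rest on the treatment-emergent definition.
2. Laboratory, ECG and vital-sign values from patients who stop drug early and come back. Protocol 9.1.1 asks them to return for scheduled assessments where they can.

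The SAP text also conflicts with itself:

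- 2.1.3.9 calls its three segments mutually exclusive, yet the day after last dose falls in both the on-treatment and the post-treatment segment.
- 2.1.3.9 bars post-treatment data other than deaths from tables, while 2.7.4 promises tables on all data after first intake.
- 2.7.7.2 counts premature-discontinuation visits for notable laboratory values, while 2.7.7 drops any such value taken more than 1 day after last dose.

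**Working it through.** The plan gives no derived figure to reproduce, because the window is a definition. The check compares the two definitions on the protocol's own calendar.

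**Inputs**

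- Protocol window: last dose + 30 days (12.5.1). SAP window: last dose + 1 day (2.1.3.9).
- Completer's last dose: Day 112, since a dose is taken at the end-of-treatment visit (Protocol 6.6.1 and Table 8-1).
- Safety call: Day 124 (Table 8-1), or 14 days after Week 16 (Protocol 9.2), which is 112 + 14 = Day 126.
- Post-baseline schedule (Table 8-1): haematology and chemistry on Days 56 and 112; ECG on Day 112; vital signs on Days 28, 56, 84 and 112.

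**Completer**

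- The SAP window ends on Day 112 + 1 = 113. The protocol window ends on Day 112 + 30 = 142.
- AE follow-up lost, call on Day 124: 124 − 113 = 11 days. That is 11/124 = 9% of the time since first dose and 11/12 = 92% of the off-drug follow-up.
- AE follow-up lost, call on Day 126: 126 − 113 = 13 days. That is 13/126 = 10% and 13/14 = 93%.
- SAE reporting time lost: 142 − 113 = 29 of 30 days. The last patients lose less, because the cut-off in SAP 2.1.1 is the last patient's last visit in the 2-week follow-up.

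**Early stopper, last dose on Day L (1 to 111)**

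A scheduled test on Day V is inside the protocol window but outside the SAP window when L + 1 < V ≤ L + 30, that is, when V − 30 ≤ L ≤ V − 2.

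| Test | Affected L | Count of 111 |
|---|---|---|
| Haematology/chemistry | 26–54 and 82–110 | 29 + 29 = 58 (52%) |
| ECG | 82–110 | 29 (26%) |
| Vital signs | 1–110 | 110 (99%) |

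Example: with last dose on Day 28, the SAP window closes on Day 29 and the protocol window on Day 58. The Day 56 bloods are summarised only under the protocol. The SAP window catches a later scheduled blood sample only when V = L + 1, which means last dose on Day 55 or Day 111.

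These counts assume attendance on the nominal days. They are shares of possible last-dose days, not of patients. As a rough scale, suppose early stopping equals the planned 10% dropout, stop days are spread evenly and everyone returns. Then 93 × 0.10 = 9.3 patients stop early, and 9.3 × 58/111 ≈ 5 have an affected blood sample.

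**The case against.** The strongest reply is that the practical effect is small.

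- The window is the same in all arms, the safety analysis is descriptive and no efficacy result changes.
- All safety data are listed, SAEs still reach the sponsor for 30 days, and all deaths after first dose are tabulated.
- The early-stopper counts weight every day equally and assume full attendance. Protocol 9.1.1 accepts telephone contact on medications and AEs as a minimum. Patients who cannot tolerate dosing, or whose code is broken in an emergency, are withdrawn from the study (Protocol 6.5.1 and 6.6.2).
- The loose wording about selected tables comes from the protocol itself.
- SAP 2.7.7.1 to 2.8.2 already mention premature-discontinuation visits, and 2.1.3.10 lets such a visit stand in for a missed one.
- The day + 1 overlap is settled in the working sections, which count that day as on-treatment.
- Protocol 9.1.1 equates one week with at least 5 half-lives, so a 30-day window includes largely drug-free time. A shorter window could be defended if it were declared.

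Much of this stands as a limit on size, and the overlap alone is minor. It does not remove the defect. A listing gives no incidence by arm. The provisions for discontinuation visits remain subject to the 1-day limit. The one-week figure does not support 1 day either, because that cut-off falls well inside the protocol's own off-drug period. A SAP may depart from the protocol, but then Section 4 has to say so and why.

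**Conclusion.** The concern holds. The protocol's window is last dose + 30 days. The SAP uses last dose + 1 day throughout its safety sections, while stating that it implements the protocol's analysis and declaring no change.

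For a completer, the main AE tables lose 11 or 13 days of follow-up, depending on which follow-up date applies, and up to 29 days for SAEs. For early stoppers, scheduled tests on days 2 to 30 after last dose are lost; how many depends on who returns and when. Tests after day 30 are off-treatment under both documents.

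AEs that began on treatment, including those that led to stopping, stay in the tables. The issue should be fixed before database lock. It bears on the completeness of the main safety tables, not on the primary analysis.

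**What to change.** - In SAP 2.1.3.9, 2.7.4, 2.7.5, 2.7.6, 2.7.7, 2.8.1 and 2.8.2, set the window from first dose to last dose + 30 days, as in Protocol 12.5.1.
- Start the post-treatment segment on the day after that window closes, which removes the day + 1 overlap.
- State that values from premature-discontinuation visits and later scheduled visits within the window are summarised.
- In 2.7.4, name the tables that use all data after first intake, and reconcile that sentence with the bar in 2.1.3.9.
- If a 1-day window is also wanted, present it as an additional table and declare it with a reason in Section 4.

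**Cost.** SAP wording and one changed flag in the analysis datasets; no new visits or data. AE counts will be slightly higher. Protocol 10.1.1 guarantees AE monitoring only to at least 14 days after last dose, so the tables need a footnote that days 15 to 30 mainly capture SAEs. The cut-off in SAP 2.1.1 will still shorten the window for the last patients, and the same footnote can say so.
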